In phase 2, we will complete a pilot randomized controlled trial comparing MAP to CBT that will allow us to estimate initial treatment effects and determine if a future, large-scale trial is warranted.

Section 6 - Specific Aims

6) Provide a statement of specific aims and hypotheses that serve as the basis for this protocol. Emphasize those aspects that justify the use of human subjects.

This proposal seeks to develop and initially evaluate an integrated, model-driven mindfulness-based intervention for chronic pain, Mindful Action for Pain (MAP), designed to help Veterans with chronic pain achieve sustained functional changes driven by personal values. To accomplish this, we have chosen the psychological flexibility (PF) model. PF refers to the ability to behave consistently with one's values even in the face of unwanted thoughts, feelings, and bodily sensations such as pain. The PF model is especially applicable to chronic pain because of its ultimate goal of supporting increased engagement in meaningful life activities. MAP is unique in that it integrates evidence-based treatment methods from Mindfulness-Based Stress Reduction (e.g., formal mindfulness meditation), Acceptance and Commitment Therapy (metaphors and experiential exercises), and Dialectical Behavior Therapy (e.g., informal mindfulness techniques) within a group-based delivery approach that is guided by the PF model. This application seeks to develop MAP (Phase 1) and conduct a pilot randomized trial of MAP vs. CBT for chronic pain (CBT-CP) (Phase 2).

Aim 1: Fully develop MAP in a population of Veterans with chronic pain (Phase 1).

Aim 2: Evaluate the feasibility of a future randomized efficacy trial of MAP vs. CBT-CP (Phase 2).

Hypothesis 1: MAP and CBT-CP will be feasible to deliver, as evidenced by attainment of recruitment goals, retention rates > 80%, and high credibility and expectancy ratings.

Aim 3: Estimate the preliminary impact of MAP and CBT-CP to determine if a future efficacy trial is warranted.

Aim 4: Explore the relationship between meditation adherence and treatment outcomes.

Aim 5: Explore objective measures of physical activity (actigraphy) at baseline and post-intervention as a potential future index of functional outcomes.

Section 7 - Background and Significance

7) Provide a succinct discussion of relevant background information to justify performing the proposed study.

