Sample size for Phase 2: In Phase 2, we will conduct 12 groups (6 MAP and 6 CBT-CP) with 7 - 8 Veterans in each group to examine the feasibility of a future RCT and preliminary response to MAP (year 3 = 4 groups; year 4 = 6 groups; year 5 = 2 groups). Anticipating up to a 20% attrition rate, 86 participants will be recruited for Phase 2.

Number of Visits: Visit 1: Consent, MINI, baseline measures and actigraphy; Visits 2 - 9: MAP or CBT-CP sessions 1 - 8; Visit 10: Posttreatment measures, actigraphy; Visit 11: 3-month follow-up measures (may be done by phone); Visit 12: 6-month follow-up interview using Microsoft Teams.

Interventions. An overview of the MAP intervention is described below, as well as the CBT-CP intervention. Both groups use an 8-week, 90-minute session protocol. The MAP intervention will be delivered solely by the PI. The PI is a licensed clinical psychologist with several years of experience conducting group and individual therapy for chronic pain using mindfulness-based techniques. For the CBT-CP intervention (Phase 2 only), we will use a manualized protocol developed at the VASDHS used in previous research (Wetherell et al., 2011). In the second half of Year 2 of the award, a part-time study therapist will be hired and trained to deliver the CBT-CP intervention. This therapist will be required to have graduate (at least master's level) training in psychology, and will be recruited within the expansive VASDHS and UCSD communities. The study therapist will be supervised by [name] (co-investigator), who is a certified CBT-CP VA provider and the current supervisor for trainees in the Behavioral Medicine clinic that provide group-based CBT-CP at the VASDHS. [name] will train the study therapist and ensure competency prior to the start of Phase 2. The study therapist will have weekly check-ins with [name] via in-person or telephone while facilitating CBT-CP groups to ensure minimal drift from the protocol and to answer any questions that arise.

Description of MAP

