
Description of CBT-CP

As aforementioned, the CBT-CP comparison group will use an 8-week, 90-minute session, manualized protocol developed at the VASDHS and used in previous research (Wetherell et al., 2011). This protocol is based on the three-component CBT model (thoughts, feelings, behaviors) with the rationale that controlling some of the factors that contribute to pain can lead to a decreased subjective experience of pain. CBT-CP focuses on training participants to manage their pain using a variety of techniques, including pain monitoring, pacing, increasing pleasant activities, progressive muscle relaxation, thought challenging, and problem skills training. The net results of these strategies is to control pain by changing its physical, cognitive, behavioral, and emotional precursors, leading to reduced pain severity and resulting beneficial consequences on pain interference, quality of life, and physical activity. Similar to MAP, CBT-CP emphasizes the importance of at-home practice assignments to develop skills taught in session.

Treatment Fidelity

Treatment fidelity is essential to the reliability and validity of study findings as well as the eventual large-scale trial and dissemination of MAP. We will employ several strategies recommended by the National Institutes of Health Behavior Change Consortium to develop a

treatment fidelity checklist for MAP during the proposed project (Bellg et al., 2004). Treatment dose across both treatment groups will be equivalent. I will conduct all MAP sessions during both phases, and the part-time study therapist will administer all CBT-CP sessions in Phase 2. Using different therapists for the MAP and CBT-CP interventions will maximize treatment adherence and minimize contamination across groups. To ensure my competency, a portion of the time during weekly meetings with [name] (co-investigator and primary mentor on CDA) will be reserved to minimize drift from the MAP protocol.

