- 3) Veterans that report suicidal ideation at assessment or baseline/post-treatment assessment via the PHQ-9 or verbally will be further evaluated by the PI and [name]. Subsequent action will depend on the level of threat presented by the Veteran and may range from making a safety plan to implementing 5150 procedures for an inpatient hold. Further, suicidal ideation will be closely monitored during treatment by clinical observation and through comprehensive suicide risk assessments, which are part of standard VA care. Participants who develop suicidality during the treatment will be evaluated by the PI and [name] to determine whether continued participation in the study is safe and clinically warranted. If we and the participant believe that continued participation is contraindicated, an endpoint evaluation will be done and the participant will be referred for appropriate treatment. Appropriate treatment will depend on level of threat, and may include recommending a different form of psychotherapy that more directly addresses the predominant concern (e.g., depression, anxiety, PTSD, sleep, etc.), a referral to the participant's primary care provider or psychiatrist for medication management, referral to the Suicide Prevention Program at the VASDHS for passive suicidality, and/or hospitalization for imminent threat of suicide.
- 4) For participants who wish to terminate prematurely, we will request a final meeting to assess clinical status and safety and to review reasons for withdrawal (if the participant is willing to share them). Referrals for alternative mental health services, including those outside this protocol, will also be provided. Participants enrolled in the study may withdraw at any time without penalty or loss of any benefits or treatment options available to them. Investigators may also withdraw a participant from the study for treatment non-compliance or a newly developed psychiatric or medical problem if, in the opinion of myself and the study team, these factors interfere with the participant's ability to participate fully in the study. If a participant discontinues the study for any reason, he/she will be offered and allowed access to any care in our clinics that any other patient not associated with the study would receive.

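### Withdrawal from the study for treatment non-compliance has no outcome assessment attached, so later outcomes can be lost selectively and within-arm change inflated

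*Combined protocol and SAP*

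**What the plan says.** Section 15 (Risk Management) describes three ways of leaving early, with different provisions for assessment.

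- **Suicidality during treatment (item 3).** If continuing is judged contraindicated, "an endpoint evaluation will be done and the participant will be referred for appropriate treatment".
- **Participant chooses to leave (item 4).** The team states that "we will request a final meeting to assess clinical status and safety and to review reasons for withdrawal". Outcome questionnaires are not mentioned.
- **Investigator decides (item 4).** "Investigators may also withdraw a participant from the study for treatment non-compliance or a newly developed psychiatric or medical problem", on the condition that, "in the opinion of myself and the study team, these factors interfere with the participant's ability to participate fully in the study". No assessment of any kind is mentioned.

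Non-compliance is not defined, and no arm is named. The speaker in item 4 is the PI, who is also the only MAP therapist: "The MAP intervention will be delivered solely by the PI" (Section 9, Interventions).

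On analysis, Section 9 (Data and Data Analysis) plans a random-intercept linear mixed model over baseline, eight weekly measures and post-intervention. It says the within-group MAP effect will help set future directions: medium-large effects count as a signal for further testing, and small ones point to more development work. Data will be examined for missing values, but no analysis set or missing-data method is named.

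**The concern.** Compliance is a consequence of the assigned treatment. A rule that lets it end study participation makes the presence of later outcomes depend on the course of treatment, which is informative loss. Section 7 gives a reason to expect a link with outcome: it cites a dose-response relation between formal meditation practice and improvement. If that holds in MAP, those removed for non-compliance are on average those who improve less, and the change estimated from the rest overstates the change in everyone assigned.

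The within-group MAP effect is the most exposed quantity, because it can be inflated whatever happens in CBT-CP and because a stated go-forward decision rests on it. Aim 4, which relates meditation adherence to outcome, would also lose participants from the low end of the adherence range.

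**Working it through.** **1. Figures that can be rebuilt.** Phase 1 has 20 participants and Phase 2 has 86, and 20 + 86 = 106, as in Sections 2a and 10. Twelve groups of 7-8 give 84-96, which contains 86. Planned attrition of up to 20% (Section 9, Sample size for Phase 2) leaves 86 x 0.80 = 68.8, about 69. The documents give no withdrawal rate for non-compliance and no outcome difference for non-compliers, so everything below uses assumed values.

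**2. Within-arm change, closed form.** Let w be the share withdrawn, c the improvement in those retained, and g the shortfall in those withdrawn. The improvement in everyone assigned is c - wg. If the withdrawn contribute nothing, the estimate is c. The overstatement is wg, or wg/(c - wg) in relative terms.

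With c = 1.2 BPI points and no improvement in non-compliers (g = 1.2):
- w = 10%: 0.12/1.08 = 11%
- w = 15%: 0.18/1.02 = 18%
- w = 20%: 0.24/0.96 = 25%

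With half that gap (g = 0.6):
- w = 10%: 0.06/1.14 = 5%
- w = 20%: 0.12/1.08 = 11%

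In SD units, w = 10-20% and g = 0.5-1.0 SD give wg = 0.05-0.20 SD.

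**3. Does the mixed model repair this by using data from before withdrawal?** The planned random-intercept model was simulated with ten time points, 1,500 per arm and 2 replicates. True change was -1.0 in both arms (negative is improvement), and withdrawn participants did 1.0 point worse and were last measured at week 4. Difference is MAP minus CBT-CP.

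| Withdrawn, MAP / CBT-CP | MAP change, full data | MAP change, after withdrawal | Difference, full data | Difference, after withdrawal | Shift in difference |
|---|---|---|---|---|---|
| 20% / 20% | -1.035 | -1.201 | -0.029 | -0.021 | +0.008 |
| 20% / 10% | -1.005 | -1.181 | -0.011 | -0.084 | -0.073 |
| 10% / 20% | -1.031 | -1.128 | -0.023 | +0.048 | +0.071 |

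The true difference is zero, so the small full-data differences are simulation noise. Within-arm inflation in MAP is 1.201/1.035 = 16%, 1.181/1.005 = 18% and 1.128/1.031 = 9%, close to the closed form. At 20%/20%, dropping the withdrawn entirely gives -1.225 in MAP instead of -1.201, so keeping the early weeks helps only slightly. A random intercept does not carry a participant's own slope forward.

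**4. Between-arm contrast.** With the same gap in both arms and the withdrawn removed, the bias towards MAP is (w in MAP - w in CBT-CP) x g. It is zero at equal rates. At 20% against 10% with g = 0.5-1.0 SD it is 0.05-0.10 SD towards MAP, and with the rates swapped it is 0.05-0.10 SD against MAP. The last column of the table shows the same pattern: nearly zero, then about 0.07 points in either direction.

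**The case against.** A reader might infer that the rule inflates MAP's advantage over CBT-CP, since the MAP therapist takes part in the decision and MAP asks for daily meditation. The documents do not support that. The rule names no arm, CBT-CP also stresses home practice (Section 9, Description of CBT-CP), and both arms log daily practice (Section 27, LifeData). Rates of 5% in CBT-CP and 15-20% in MAP, with compliers improving 1.2 points and non-compliers none, do bias the mixed-model contrast by 0.12-0.17 points towards MAP. But those rates are chosen, and reversing the imbalance reverses the sign.

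A reader might also infer that such withdrawals could be left out of the retention target ("retention rates > 80" per cent, Hypothesis 1). Section 9 rules this out: retention is counted as those who attend and complete out of those who began, so a starter who is withdrawn counts as not retained. Discretionary withdrawals therefore work against the team's own feasibility criterion.

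Other points against also have weight:
- The rule is permissive and conditional. Loss of outcomes is inferred from silence, and nothing says that data already collected are discarded.
- Weekly BPI is polled at the start of sessions (Section 9.8), so a non-attender loses those values anyway. For such a participant the rule mainly removes the post-intervention point from the ten-point model, plus the 3-month visit, which is outside it. The simulation charges all loss after week 4 to the rule and so overstates its separate contribution.
- A 10-20% withdrawal rate for this reason alone would use half to all of the planned attrition from every cause.
- Section 9 already plans to record reasons for discontinuation and to compare missingness and retention between arms.
- Effect sizes are to be read with caution, as suits a pilot.

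These points limit the size and remove any claim about direction between arms. They do not close the gap: comparing missingness by arm describes the loss but cannot recover outcomes that were never collected.

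**Conclusion.** The point holds in limited form. The protocol lets the study team end study participation for non-compliance and specifies no later outcome assessment, although it makes some provision for the other two kinds of exit. This risks informative loss of post-intervention and 3-month outcomes.

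If non-compliers improve less, within-arm change is inflated, illustratively by about 10-25% at 10-20% withdrawal, or 0.12-0.24 points against the plan's 1-point important change. That rests on assumed rates and on no improvement at all in non-compliers; half the gap gives 5-11%. The documents suggest the link between compliance and outcome through the dose-response premise but do not establish it for this trial.

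The MAP versus CBT-CP contrast is biased only if withdrawals differ by arm in frequency or in relation to outcome. No such imbalance is shown, and the direction is unknown. This is a cheap improvement worth making, not a flaw that invalidates the pilot.

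**What to change.** Add to Section 15, item 4, and to the Phase 2 analysis text in Section 9:

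1. Stopping sessions, for whatever reason and whoever decides it, does not end study participation. Unless consent is withdrawn, the participant is still asked for the post-intervention and 3-month assessments, and for weekly BPI where feasible.
2. All such participants are analysed in the arm to which they were assigned, with every available measurement.
3. Investigator-initiated withdrawals are reported separately by arm, with the reason. They already count as not retained, so the retention definition needs no change.

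The routes exist: the 3-month visit may be done by phone (Section 9, Number of Visits), Qualtrics is offered for post-program questionnaires (Section 27.2c1), and the COVID-19 procedures in Section 9 allow questionnaires by telephone. Weekly BPI is left optional because it is collected in session and would need a new route for people who do not attend. The cost is a short protocol change and a few extra remote assessments by existing staff. With complete follow-up this source of bias would disappear; partial follow-up would reduce it. The clinical grounds for stopping sessions are not in question.

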and any related protections or assurances to prohibit or avoid identification. Describe how the number of people with access to identifiers for research purposes is limited in order to protect a participant's privacy.

Participants will be identified by subject numbers, which will be stored separately from coded data. Research team members will identify participants for purposes of communication about the study (scheduling, assessments), documentation (e.g., CPRS notes) and safety (e.g., identifying SAEs or AEs). Only staff with direct contact with participants will have access to identifiers.

Interview responses may be recorded by the assessor from a remote location in an electronic format (electronic form behind the VA firewall).

Electronic research data will include responses on self-report assessment surveys. Research data will be collected by phone or the LifeData app and will be entered into an electronic data set stored on VA secure local research servers accessible only by authorized users on password-protected computers.

LifeData

Participants will receive a unique 5-digit LifeData ID to access the LifeData application. This 5-digit ID will be separate from the participant's study ID, ensuring separation of identifiers and data. A participant crosswalk that links the study ID and 5-digit LifeData ID to the participant's name and user name will be securely stored electronically in the study directory in a password-protected Excel document. Only research staff, approved by the IRB, can access the study directory.

Participants will use the LifeData mobile app to access guided meditation recordings (in the MAP group only) and log daily practice (both MAP and CBT-CP groups). Participants will download the app on their personal mobile device. When participants log into the app on their phones, participants will be given a unique 5-digit code (LifeData ID). De-identified data collected from the app are encoded and encrypted before it is sent to an encrypted storage database located in the US. Data are encrypted before being pushed to the storage database. No data are ever stored on the server's file server but always in the database. Once in the database, data are stored in an encrypted manner. Access to data is gated so entry is only permitted to users entering through the approved route (i.e., the database cannot be hacked into by guessing at the URL).

Additional steps to ensure confidentiality include: confidentiality training for research staff; identifying subjects by an arbitrary number; filing ID number key lists separately from data; omitting participant names from any forms; using an acronym in return addresses on any correspondence to participants; storing all data in locked file cabinets; securing all computers that store data; storing electronic data on secure servers behind firewalls. This study will use LifeData's "Anonymous Mode," which does not require participants to input a valid email address or any other identifiable information. All research staff will fulfill the educational requirements set forth by VA.

27.b) Entry of a CPRS Research Informed Consent Note is required when subjects will be admitted as inpatients or treated as an outpatients for research and the study involves research medical care or may affect medical care.

- *If a Research consent Note is required, then a Research Progress Note should also be entered for each procedure or intervention.*
- *Scanning the Consent and HIPAA Authorization into CPRS is not required. Linking the Consent to the Research Informed Consent Note may be permitted and can be useful for trials involving the Research Pharmacy or when research will be performed in conjunction with clinical procedures.*
- *For Non-Veterans, if Research Informed Consent Notes are entered, then the NOPP Acknowledgment must be scanned into the record. Otherwise a copy of the signed NOPP must be retained with the Investigator's research records and a copy sent to the Privacy Officer; see the ? Help for more information.*

27.b1) Is entry of CPRS notes required based on the above criteria?

- CPRS notes are needed for ALL subjects
- CPRS notes are needed for SOME subjects
- CPRS notes are NOT needed for any subjects

27c) Select the VA Sensitive Information (VASI) use category

- This study does not collect or use any VASI
- This study uses but does not save, collect, copy, or record VASI
- This study does collect or record VASI

Section 27.1 VA Sensitive Information (VASI)**27.1a) For each type of VASI, indicate all that apply:**

Indicate which of the following will be collected/recorded:

- Protected Health Information (PHI)
- Names
- Device identifiers and serial numbers
- E-mail addresses
- Medical record numbers
- URLs (Universal Resource Locator)
- All elements of dates (except year) or any age over 89
- Health plan beneficiary numbers
- IP Addresses (Internet Protocol)
- Telephone numbers
- Account numbers
- Biometric Identifiers including finger and voice print
- Fax numbers
- Certificate or license numbers
- Full face photographic images and comparable images
- All geographic subdivisions smaller than a state
- Vehicle ID and serial numbers including license plate numbers
- Social security numbers or scrambled SSNs (describe below)
- Other unique identifying number, characteristic, or code (describe below)

27.1a1) Describe why SSN are needed for this study

Participant payment and chart access

27.1b) Consent Forms and/or HIPAA Authorization

- Yes
- No

27.1c) Images with personal identifiers are used for this study (x-rays, MRI images with patient names, record numbers, dates, etc.)?

- Yes
- No

27.1c1) Identify where images will be stored (e.g., in the medical record, with study hardcopy records, with study electronic VASI records).

PI's research drive

27.1d) Photos with faces or audio video recordings are used for this study.

Yes No

27.1d1) Identify the device or devices that will be used to take/make the photographs or recordings.

As described in section 9.11, we use the Sony ICDPX312 Digital Voice Recorder to record treatment sessions, which is compliant with VHA regulations and often used at VASDHS for research and clinical purposes.

27.1d2) Identify where images will be stored (e.g., in the medical record, with study hardcopy records, with study electronic VASI records

PI's research drive

27.1e) Biological specimens with identifiers are used for this study.

Yes No

Section 27.2 Data Collection, Tools, and Resources

27.2a) Will any specially obtained software be used?

Yes No

27.2b) Will any mobile devices (laptop, tablet, portable hard-drive, etc.) be used in support of this study?

Yes No

27.2b1) Provide details of the device/s. Indicate whether the device is FIPS 140-2 encryption validated and confirm that the device is listed in the VA EIL. Provide details regarding the nature of the data that will be stored or transmitted on the device and confirm whether a copy of all data will be stored on the VA network.

Participants will have the option to use the LifeData mobile app to access guided meditation recordings and log daily practice (participants will also have option to access guided meditation via CD and log using paper and pencil, if they prefer). Participants will download the app on their personal mobile device. When participants log into the app on their phones, participants will be given unique 5-digit codes (LifeData ID). De-identified data collected from the app are encoded and encrypted before it is sent to an encrypted storage database located in the US. Data are encrypted before being pushed to the storage database. No data are ever stored on the server's file server but always in the database. Once in the database, data are stored in an encrypted manner. Access to data is gated so entry is only permitted to users entering through the approved route (i.e., the database cannot be hacked into by guessing at the URL).

Participants will be provided with a unique 5-digit LifeData ID to access the application, which will be distinct from participant's study ID, ensuring separation of identifiers and data. A participant crosswalk that links the study ID and 5-digit LifeData ID to the participant's name and user name will be securely stored electronically in the study R-drive in a password-protected Excel document. Only research staff, approved by the IRB, can access the study R-drive.

27.2c) Does the study require use of an electronic data capture system?

Yes No

27.2c1) Provide the web address, details regarding their security features, the nature of the data involved, and the research purpose. Also include a description of how VA retains a copy of the data entered into the system.

Data collected on the LifeData mobile application are made accessible to the researchers only by directly accessing the secure site (<https://server.lifedatacorp.com>) and downloading the dataset as a CSV file. Data are encrypted in transmission with TLS 1.2 or greater. Datasets are never transmitted by email. Only study personnel communicating with Veterans (e.g., providing support for the mobile app; arranging appointments) will have direct access to identifiable data. Participants will be given the option of using Qualtrics to complete baseline and post-program questionnaires. Information about Qualtrics is available here: <https://www.qualtrics.com> and <https://vhaordfedramp.gov1.qualtrics.com>. Qualtrics enables accessible and user-friendly collection of patient-reported outcome survey data for research studies using remote procedures. Study participants are sent a link to a Qualtrics survey by study staff and can complete their survey on any internet-connected device with an internet browser. Qualtrics is accredited by FedRAMP, a government-wide initiative to protect sensitive data in federal agencies, ensuring gold standard security for data collected through Qualtrics. Further information can be found at <https://qualtrics.com/platform/fedramp>. Researchers will access participant data using the Qualtrics dashboard, and all data will be identified through a numeric participant code only. Only approved members of the research team have access to the secure dashboard. Research team members will export participant data from the dashboard directly to secure VA research servers (i.e., the R drive).

27.2d) Will any other web-based applications be used (e.g., for recruitment, completing online questionnaires, or processing data)?

Yes No

27.2e) Will coded data that excludes personal identifiers be used? Coded data excludes *all* HIPAA identifiers (per VHA Handbook 1605.1 Appendix B), including dates

Yes No

27.2e1) Identify where the code key is stored and in what format (electronic, paper).

Coded key will be stored on paper in a locked cabinet in a locked office and in a file separate from data on the PI's research drive.

A participant crosswalk that links the study ID and 5-digit LifeData ID to the participant's name and user name will be securely stored electronically in the study directory in a password-protected Excel document.

Section 27.3 Data Sharing and Transportation

27.3a) Does this study involve collecting, sharing or transporting any type of data outside of the local VA?

Yes No

Section 27.4 Research Record Storage and Retention

For each type of record, indicate whether it is collected for this study

27.4a) Hardcopy records/data (includes paper, pictures, film, etc.)

Yes No

27.4a1) Identify precisely where hardcopy data will be stored to include physical site, building, and room number, etc. For each location identify whether VASI or non-sensitive information is stored at that location. For VASI, identify how the data is secured.

VMRF room 242 in locked cabinet

27.4a2) Are all of the above locations at VA?

Yes No

27.4b) Electronic study records (includes computer files, removable disk files, digital files, etc.).

Yes No

27.4b1) Identify precisely where **non-sensitive** electronic records/data will be stored to include the full map drive, network location/server name, etc., and a brief description of what data/information is stored at each location.

R:/[name]

Data collected on the mobile application are made accessible to the researchers only by directly accessing the secure site (<https://server.lifedatacorp.com>) and downloading the dataset as a CSV file. Data will then be permanently deleted from the LifeData secure server.

27.4b2) Identify precisely where **VA** electronic records/data will be stored to include the full map drive, network location/server name, etc., and a brief description of what data/information is stored at each location.

If no VASI is collected or recorded for this study, simply indicate that the “Study does not collect or record VASI”.

R:/[name]

27.4b3) Are any of the locations described in 27.4b outside of the VA Secure Network? *Note: this includes storage on a computer local hard drive.*

Yes No

27.4b4) Describe the storage method (e.g., in a VA encrypted laptop) and security details, including the device /media location and ownership; describe backup procedures; identify the web applications; security features; and the nature of the data involved. Identify the rationale for needing to store data outside of the VA Network and describe the arrangement and authority (MOU, contract, other) to permit the arrangement.

Daily tracking of homework will be collected via a mobile device and temporarily stored on the LifeData secure sever. Participants' responses are always encrypted inside the app and as they travel from the participants' phones to the LifeData server. Their responses are also encrypted in the LifeData server. All data in the LifeData server is encrypted using several techniques that include AES 256 bit encryption and TLS encryption 2.0 or greater.

Data being transmitted from the participant's phone to the LifeData server is first encoded using Base 64 and then encrypted using AES 256 bit encryption. Synchronous and asynchronous SSL encryption is used between the LifePak Builder and Manager (<https://server.lifedatacorp.com>), where assessment schedules are created. The LifePak Builder and Manager can only be accessed after supplying a verified user ID and password.

Once downloaded to VA computers, all digital files will be stored in the study directory in the secure VA network.

27.4c) Record Retention - VHA requires compliance with Records Control Schedule (RCS-10) for retention of electronic and hard copy records. Following study closure, these temporary records must be retained for six years and then destroyed. Longer retention may be permitted if required by other Federal regulations or requirements. Will RCS-10 requirements be followed (i.e., 6-year retention)?

I will adhere to VHA Records Control Schedule-10 requirements
 I request an exception to RCS-10 requirements

Section 27.5 Additional Privacy or Information Security Details

Provide any other privacy or information security details here.

None

Section 27.6 Attestations

In the event of real or suspected breach of security, the Information Security Officer, Privacy Officer, VA Police (if appropriate), and the individual's supervisor will be notified within one hour of learning of the event.

Agree Disagree

Study staff will be up to date on any required VHA Privacy Policy and Information Security training or they will not be allowed access to VA Sensitive Information.

Agree Disagree

Access to research sensitive information, if any, will be removed when study personnel are no longer part of the research team.

Agree Disagree

At least one copy of all study records (whether sensitive or non-sensitive) will be retained under VA control and only destroyed in compliance with the approved Records Control Schedule

Agree Disagree

The VA retains ownership of the research data. Should the investigator leave the VA, custody of the research records will be assigned to another investigator and the Research Service notified in writing, or custody of the

research records will be transferred to the Research Service.

Agree Disagree

Section 28 - Protocol Association to New or Existing Project

28) Is this a new R&D Project? Before you go on to complete the *Initial Review Submission Form* (which is used for attachments), please address the association of this Protocol to an R&D Committee Project. This Protocol may represent a new R&D Project, or it may be an additional Protocol under an existing R&D Project (such as when a single grant supports multiple Protocols). Will this Protocol be submitted to the R&D Committee as a new Project?

Yes No

Section 29 - Existing Project Association

29) The associated R&D Project should already exist in the database. Identify the R&D Project(s) that correspond to this protocol.

Project Status	Proposal Number	Project Title	Principal Investigator	
No Projects are Linked to this Study				

The Protocol Application is now complete for a Protocol attached to an existing Project.

Next you will go on to the Initial Review Submission Form. This form is used to collect the Application and any other needed attachments for submission to the IRB for review.

Press *Save and Continue*
